### 1.4.2. Pharmacokinetics

As of September 30, 2020, PK data were available from 181 patients enrolled in the LOXO-BTK-18001 study. Steady-state PK parameters of LOXO-305 in these cancer patients could be derived from data collected on Cycle 1 Day 8 (Figure 1), and are shown in Table 1. These data show that LOXO-305 is absorbed after oral administration with a median time to maximum observed plasma concentration ( $t_{max}$ ) of approximately 2 hours and low clearance (Table 1). Due to the limited sampling interval (0-8 hours), imputation for the 24-hour sample was made from Cycle 1, Day 8 predose sample, leading to an estimated plasma half-life of approximately 20 hours. Maximum observed plasma concentration and area under the plasma concentration-time curve (AUC) of LOXO-305 showed an increase proportional to dose (Figure 2). Following administration of the recommended Phase 2 dose (RP2D) 200 mg QD, mean trough plasma levels of LOXO-305 exceeded the concentration required for 96% inhibition of BTK in vitro ( $IC_{50} = \text{CCI}$  ng/mL,  $IC_{96} = \text{CCI}$  ng/mL). Further details may be found in the IB.

Pharmacokinetic data following oral administration of a 200-mg dose of LOXO-305 in tablet form in healthy volunteers in the LOXO-BTK-20014 study indicate that there was little effect of either a standard meal or the proton pump inhibitor (omeprazole) on the PK of LOXO-305.

**Table 1: Pharmacokinetic Parameters of LOXO-305 in Cancer Patients (Study LOXO-BTK-18001) at Steady State (Cycle 1 Day 8)**

Dose Level	N	$C_{max}$ (ng/mL) Geo mean (%CV)	$t_{max}$ (h) Median (min, max)	$AUC_{0-8}$ (ng*h/ mL) Geo mean (%CV)	$AUC_{0-24}$ (ng*h/mL) Geo mean (%CV)	CL/F (L/h) Geo mean (%CV)	$t_{1/2}$ (h) Geo mean (%CV)	Ratio $AUC_{0-8}$ Day 8/Day 1 Geo mean (%CV)
25 mg QD								
50 mg QD								
100 mg QD								
150 mg QD								
200 mg QD								
250 mg QD								

[figure not shown]
Dose Level	N	C max (ng/mL) Geo mean (%CV)	t max (h) Median (min, max)	AUC 0-8 (ng*h/ mL) Geo mean (%CV)	AUC 0-24 (ng*h/mL) Geo mean (%CV)	CL/F (L/h) Geo mean (%CV)	t 1/2 (h) Geo mean (%CV)	Ratio AUC 0-8 Day 8/Day 1 Geo mean (%CV)
300 mg QD	CCI							

[figure not shown]

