#### 7.2.1. Adverse Events

Adverse event definitions; assignment of severity, causality, action taken, and outcome; and procedures for reporting SAEs are detailed in [Appendix 1](#).

Subjects will be asked a non-leading HDYF? question such as “Have there been any changes in your health status since Screening/since you were last asked?” at the timepoints specified in [Appendix 4](#) (ie, at Screening [after the ICF is signed], at Check-in [Day -1], at each postdose vital sign measurement, and at an appropriate time for all other days). Subjects will also be encouraged to voluntarily report AEs occurring at any other time through the EOS.

Adverse events, whether volunteered, identified by the subject’s responses to HDYF? inquiries, or noted on physical examination, ECG, vital sign measurements, or clinical laboratory evaluations, will be recorded throughout the study (ie, from signing of the ICF until EOS [or ET if the subject discontinues from the study and does not complete a follow-up phone call]), either as subject medical history (if the event is reported as beginning prior to signing of the ICF or if the event occurs prior to study drug administration on Day 1 and is assessed as not related to study procedures by the Investigator [or designee]) or as AEs (if the event occurs after signing of the ICF but prior to study drug administration on Day 1 and is assessed as related to study procedures by the Investigator [or designee], or if the event occurs after study drug administration on Day 1 through EOT or ET regardless of relationship to study drug). From EOT or ET through EOS, only AEs assessed as related to study drug by the Investigator (or designee) are to be reported. All SAEs that develop from the time of ICF signing until EOS (or ET, if the subject discontinues from the study and does not complete a follow-up phone call) are to be reported.

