Unless a subject withdraws consent or is withdrawn from the study and does not complete the follow-up phone call, all subjects must be followed until EOS. Subjects with AEs that are assessed as related to study drug by the Investigator (or designee) which are ongoing at EOS may continue to be followed until the symptoms or value(s) return to normal, or acceptable levels, as judged by the Investigator (or designee) and confirmed by the Sponsor. The Investigator (or designee) should use appropriate judgment in ordering additional tests as necessary to monitor the resolution of events. The Sponsor may request that additional safety tests be performed.

Subjects will receive a follow-up phone call 7 days ( $\pm$  2 days) after EOT or ET to determine if any SAE or drug-related AE has occurred since the EOT or ET visit.

At all times, a subject may be required to remain at the CRU for longer at the discretion of the Investigator (or designee).

Any event that meets the criteria of a suspected unexpected serious adverse reaction (SUSAR) will be reported to the Institutional Review Board (IRB) according to CRU policy by the Investigator (or designee) and to regulatory authorities by the Sponsor (or Sponsor designee) according to regulatory authority requirements. Refer to Reference Safety Information in the current IB for LOXO-305 for additional safety information. 

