## **Appendix 4: Schedule of Assessments**

Study Procedures a	Screening (Days -29 to -2)	Check-in (Day -1)	Study Conduct		CRU Discharge/ EOT or ET t	Follow-up Phone Call (EOS)
			Day 1	Days 2 to 7	Day 8	7 (± 2) days post EOT or ET v
Confined to the CRU		X	X	X	X	
Inclusion/Exclusion Criteria	X	X				
Informed Consent	X					
Demographics	X					
Medical History	X	X b				
Height/Weight/BMI	X c	X c				
Physical Examinationd	X	X			X	
12-Lead ECGe	X	X	X	X	X	
Vital Signsf	X g,h	X g,h	X h	X	X g,h	
HDYF? Inquiryi	X	X	X	X	X	X
AEs/SAEsj	X	X	X	X	X	X
LOXO-305 Dosek			X			
CCI						
Clinical Laboratory Evaluationsn	X	X		X u	X u	
COVID-19 Testo	X	X				
eGFR	X	X				
Hepatitis and HIV Screen	X					
HbA1c Test	X					
Drug Screenp	X	X				
Prior and Concomitant Medicationsq	X	X	X	X	X	X
Pregnancy Testr	X	X		X u	X u	
FSH Tests	X					
TSH Test	X					

Abbreviations: AE = adverse event; BMI = body mass index; BP = blood pressure; COVID-19 = SARS-CoV-2; CRF = Case Report Form; CRU = Clinical Research Unit; ECG = electrocardiogram; eGFR = estimated glomerular filtration rate; EOS = End of Study; EOT = End of Treatment; ET = Early Termination; FSH = follicle-stimulating hormone; HbA1c = hemoglobin A1c; HDYF? = How Do You Feel?; HIV = human immunodeficiency virus; ICF = Informed Consent Form; PK = pharmacokinetic; SAE = serious adverse event; TSH = thyroid-stimulating hormone; UA = urinalysis.

- a. For details on study procedures, see [Section 7](#).
- b. Interim medical history only.
- c. Height collected at Screening only; BMI based on Screening height.
- d. A complete physical examination will be performed at Screening and EOT (Day 8, 168 hours postdose) or ET. An abbreviated physical examination will be performed at Check-in (Day -1).

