- o. Testing for COVID-19 will be conducted at a minimum of Screening and Check-in (Day -1). Testing for COVID-19 may also be conducted periodically during the subject's CRU confinement, at the discretion of the Investigator (or designee). Tests will be performed by rapid polymerase chain reaction or antigen testing (or equivalent, as determined by the Investigator [or designee] with agreement from the Sponsor).
- p. Drugs of abuse urine test, including cotinine (matched-control healthy subjects only) and alcohol (urine or breath test). Results from the drugs of abuse tests will be used to determine subject eligibility per the inclusion/exclusion criteria.
- q. Prior and concomitant medication administration will be recorded beginning at informed consent. In addition, all Investigator-approved medications taken by a subject within 30 days prior to Day 1 for prescription medications (for renal impairment subjects only), and for all prescription and over-the-counter medications, those taken 14 days or 5 half-lives (if known), whichever is longer, prior to Day 1 will be recorded on the subject's electronic CRF.
- r. Female subjects only. Performed at Screening, Check-in (Day -1), and Day 7 (144 hours postdose), if the subject completes the study (EOT) or on the day of ET. Pregnancy tests will be performed on the day prior to subject release from the CRU if the subject completes the study (EOT).
- s. Post-menopausal female subjects only.

- t. EOT is defined as when the subject is released from the CRU following completion of all assessments through Day 8. ET is defined as when the subject is released from the CRU if the subject terminates the study early. Vital sign measurements, ECG, and physical examination results are to be available for review by the Investigator (or designee) prior to subject release from the CRU at the EOT visit (Day 8) or ET. Clinical laboratory results (for clinical chemistry, hematology, coagulation, and UA) and pregnancy test results (female subjects only) are to be available for review by the Investigator (or designee) prior to subject release from the CRU at the EOT visit and prior to subject release from the CRU at the ET visit if available.

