- u. Clinical laboratory evaluations and pregnancy test (female subjects only) will be performed on the day prior to subject release from the CRU (Day 7) if the subject completes the study (EOT). Clinical laboratory evaluations and pregnancy test (female subjects only) will be performed on the day of subject release from the CRU if the subject terminates early (ET).
- v. To be conducted 7 days ( $\pm$  2 days) following EOT or ET. EOS is defined as when the subject is contacted for a follow-up phone call 7 days ( $\pm$  2 days) after the EOT visit or ET visit to determine if any SAE or study drug-related AE has occurred since the EOT or ET visit. All subjects who received LOXO-305 (including subjects who are terminated early) will receive a follow-up phone call.

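### For non-serious AEs, recording regardless of relationship stops at release from the unit, so a dosed subject who leaves early has a shorter all-cause window than a completer

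*Protocol*

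**What the plan says.** Protocol Section 7.2.1 classes an event as an AE "if the event occurs after study drug administration on Day 1 through EOT or ET regardless of relationship to study drug". After that point, "From EOT or ET through EOS, only AEs assessed as related to study drug by the Investigator (or designee) are to be reported". SAEs are handled separately: they are reported whatever their relationship until EOS, or until ET for a subject who discontinues and does not complete the call. The same rules appear in the Synopsis, Section 3.1, Appendix 4 footnote j and SAP Section 4.

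Appendix 4 footnote t ties both endpoints to leaving the unit: "EOT is defined as when the subject is released from the CRU following completion of all assessments through Day 8", and "ET is defined as when the subject is released from the CRU if the subject terminates the study early". Footnote d gives the nominal time for completers: "A complete physical examination will be performed at Screening and EOT (Day 8, 168 hours postdose) or ET". No minimum time after the dose is attached to ET.

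The follow-up call comes 7 (± 2) days after EOT or ET. Its stated purpose is "to determine if any SAE or drug-related AE has occurred since the EOT or ET visit", and "All subjects who received LOXO-305 (including subjects who are terminated early) will receive a follow-up phone call". The Appendix 4 table also marks the HDYF? inquiry and the AE/SAE row at that call.

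On the analysis side, SAP Section 7.2 keeps every dosed subject in the Safety Population. SAP Section 8.6.1 summarises TEAEs as frequencies by renal function group; it sets no end to the TEAE window and makes no adjustment for time observed.

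**The concern.** Completers and early terminators share a denominator but not a recording window. Once an early terminator leaves the unit, a non-serious AE enters the data only if it is rated related, whereas the same event in a subject still confined is recorded whatever its rating. Crude frequencies then treat the two subjects as equally observed.

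Two features could make this more than random loss. Protocol Section 4.6 lists AEs among the reasons for withdrawal, so early exit may be informative. In addition, the two-category scale in Appendix 1 reserves the related category for events with no other identifiable cause, such as comorbidity or concomitant drugs. Renally impaired subjects may have both, while the controls are screened for good health. The post-ET filter could therefore remove more events from the impaired groups, in an open-label study. At stake is how comparable the groups' tabulated TEAE frequencies are, when each impairment group holds at most 8 subjects.

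**Working it through.** **Inputs**
- Dose on Day 1; EOT on Day 8, 168 h postdose (Protocol Section 3.1; Appendix 4 footnote d).
- ET = release on early termination, at t hours postdose, with no minimum (Appendix 4 footnote t).
- Call 7 (± 2) days after EOT or ET (Section 7.2.1; Appendix 4 footnote v).
- Up to 8 per impairment group and up to 24 in Group 1 (Section 4.5, Table 2).
- Half-life in cancer patients: "leading to an estimated plasma half-life of approximately 20 hours" (Section 1.4.2).

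**1. The plan's own figures.** (8 − 1) × 24 = 168 h, as stated. Participation: 28 (Days −29 to −2) + 9 (Days −1 to 8, no Day 0) + 9 (7 + 2) = 46 days, as stated. At a 20 h half-life, 168/20 = 8.4 half-lives.

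**2. All-cause window for non-serious AEs.** A completer has 168 h, nominally, since Section 7.2.1 allows a longer stay. An early terminator has t, a share of t/168:

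| ET at | Share of completer window | Call, earliest (t + 120 h) | Call, nominal (t + 168 h) |
|---|---|---|---|
| 6 h | 3.6% | 126 h | 174 h |
| 24 h | 14.3% | 144 h | 192 h |
| 48 h | 28.6% | 168 h | 216 h |
| 72 h | 42.9% | 192 h | 240 h |

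**3. Can the existing call cover 168 h?** At the nominal 7 days, t + 168 is never below 168 h. On the earliest permitted day, t + 120 < 168 only when t < 48 h. A condition that the call be no earlier than 168 h postdose needs a gap of at most 168 − t hours after ET. That is always under 168 h, so it lies inside the upper limit of 9 × 24 = 216 h.

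**4. Effect on a group of 8 (illustration only).** If one of 8 leaves at 24 h, all-cause person-time is (7 × 168 + 24)/(8 × 168) = 1,200/1,344 = 89.3% of full. Assume a constant hazard and a 30% risk over 168 h of a non-serious, unrelated-rated AE. The early leaver's recorded risk is 1 − 0.7^(24/168) = 0.050, and the expected crude incidence is (7 × 0.30 + 0.050)/8 = 26.9% instead of 30%. If two of 8 leave at 24 h, it is (6 × 0.30 + 2 × 0.050)/8 = 23.7%. Neither the 30% nor the number leaving comes from the documents.

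**5. Largest change from one missed event.** 1/8 = 12.5 points in a group of 8, or 1/24 = 4.2 points if Group 1 reaches 24. Either applies only if the subject had no earlier TEAE.

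**The case against.** The rule is stated consistently and looks deliberate: record everything during confinement, then SAEs and related AEs only. Much is still covered. An event that causes withdrawal normally starts before ET and so falls inside the all-cause window. ET assessments are attempted, the Investigator may extend the stay, and both SAEs and related AEs run to EOS if the call is completed. No inferential safety analysis is planned. All of this stands, and it confines the gap to non-serious, unrelated-rated events between ET and 168 h.

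Some stronger readings are tempting but not supported:
- *That the secondary objective is a between-group comparison of TEAEs.* It is to evaluate safety and tolerability in both populations. Only the primary, PK objective is worded as a comparison.
- *That a quarter of a group may leave early.* The figures of up to 8 enrolled and at least 6 completing are a recruitment ceiling and a goal. They are not an early-exit rate. SAP Section 8.1 also ties completion to the EOS visit, so a subject observed for the full 168 h who misses the call is a non-completer too.
- *That the call cannot elicit unrelated events.* Its stated purpose is narrow, but the open HDYF? question is already scheduled at it. What excludes unrelated events is the recording rule.
- *That the call routinely falls before 168 h.* This needs both an ET before 48 h and use of the early part of the call window.
- *That drug-related events are lost while drug is still present.* Under mono-exponential decline with a 20 h half-life, about 0.5^(24/20) = 44% remains at 24 h. Related events are nevertheless collected to EOS, so residual drug matters only if relatedness is misrated, and the documents give no basis for sizing that.

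It can also be said that a fixed window would not fully equalise ascertainment, because one recalled report is not daily in-clinic inquiry. That is true, and it argues for showing observation time alongside the extended window.

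**Conclusion.** The point holds for non-serious AEs. An early terminator's all-cause window equals the time to release, against a nominal 168 h for completers, and nothing in the protocol or SAP equalises the two or reports the difference. Under-recording is limited to unrelated-rated, non-serious events that start after ET and before 168 h. Its expected size is unknown because no ET rate or timing is given; in a single-dose, confined study with descriptive safety it is probably small. The window shares follow directly from the text, while the incidence figures rest on an assumed hazard and assumed exits. Differential filtering by group is plausible from the relatedness definition but is not demonstrated. Low severity: a cheap improvement that slightly reduces bias.

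**What to change.** Anchor the window to the dose. In Protocol Sections 3.1 and 7.2.1 (with the matching Synopsis text), Appendix 4 footnotes j and v, and SAP Section 4:
- Record all AEs regardless of relationship through 168 h postdose (nominal Day 8) for every dosed subject who remains contactable, and start the related-only rule after that.
- For ET subjects, make the already scheduled call no earlier than 168 h postdose, and record all AEs with onset up to 168 h that the HDYF? inquiry at that call elicits. After 168 h, the present rules for related AEs and SAEs apply.
- List the post-dose observation time for any ET subject, so that a reader can see where a crude frequency rests on shorter follow-up.

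The cost is wording and one changed recording rule. It adds no visit or sample, and the timing condition fits inside the existing call window. Two limits remain: post-ET events will rest on recall, and subjects who withdraw consent cannot be covered. The observation-time listing is there for both.

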### **7.2.2. Clinical Laboratory Evaluations**

Clinical laboratory evaluations (clinical chemistry panel [fasted at least 8 hours; at ET or the day before EOT, subjects are not required to be fasted prior to clinical laboratory evaluations], coagulation parameters, hematology panel, TSH [Screening only], HbA1c [Screening only], eGFR [Screening and Check-in], and UA) will be collected at the timepoints specified in [Appendix 4](#).

Screens for HCV antibody, HBsAg, HBV IgM core antibody, and HIV antibody will be performed at Screening.

Testing for COVID-19 via PCR or antigen testing (or equivalent, as determined by the Investigator [or designee] with agreement from the Sponsor) will be performed at the timepoints specified in [Appendix 4](#). Testing for COVID-19 may also be conducted periodically during the subject's CRU confinement, at the discretion of the Investigator (or designee). Further details regarding COVID-19 testing (including procedures for subjects who test positive at any time throughout CRU confinement) are specified in a separate document.

A urine drug screen for selected drugs of abuse (including cotinine [matched-control healthy subjects only] and alcohol [urine or breath test]) will be performed at Screening and repeated at Check-in (Day -1) for all subjects. A serum qualitative or urine qualitative pregnancy test (female subjects only [quantitative serum human chorionic gonadotropin tests may be used for confirmation as needed and post-menopausal subjects may be eligible for participation if the results of the qualitative serum pregnancy or qualitative urine pregnancy test are positive but the quantitative serum human chorionic gonadotropin results are within the laboratory's reference ranges for post-menopausal women]) and an FSH test (post-menopausal female subjects only) will be performed at the timepoints specified in [Appendix 4](#).

The number of blood samples and total blood volume required for clinical laboratory evaluations is presented in [Appendix 3](#). A list of the specific evaluations is in [Appendix 2](#).

### **7.2.3. Vital Signs**

Vital sign measurements (including body temperature, respiratory rate, oxygen saturation, supine BP, and pulse rate) will be obtained at the timepoints specified in [Appendix 4](#).

Blood pressure and pulse rate measurements should be performed using the same arm for each reading and measurements should be taken after the subject has been resting in the supine position for at least 5 minutes.

When vital sign measurements are scheduled at the same time as blood draws, the blood draws will be obtained at the scheduled timepoint, and the vital sign measurements will be obtained prior to and as close as possible to the scheduled blood draw.

### **7.2.4. 12-lead Electrocardiogram**

A 12-lead ECG (including heart rate, PR, RR, QRS, and QT interval parameters) will be obtained after the subject has been resting for at least 10 minutes in the supine position at the timepoints specified in [Appendix 4](#). The QT interval will be corrected for heart rate by Fridericia's ( $QTcF = QT/[RR]^{1/3}$ ) formula.

When 12-lead ECGs are scheduled at the same time as blood draws, the blood draws will be obtained at the scheduled timepoint, and the 12-lead ECGs will be obtained prior to and as close as possible to the scheduled blood draw.

### **7.2.5. Physical Examination**

A complete or abbreviated physical examination will be performed at the timepoints specified in [Appendix 4](#). Complete physical examinations will evaluate general appearance and the following body systems/organs: dermatological; head and eyes; ears, nose, mouth, and throat; pulmonary; cardiovascular; abdominal; lymphatic; musculoskeletal/extremities; and neurological. Weight and height will be reported (height only reported during Screening). Abbreviated physical examinations will evaluate general appearance and the following body systems/organs: dermatological; pulmonary; cardiovascular; abdominal; and neurological.

## 8. SAMPLE SIZE AND DATA ANALYSIS

### 8.1. Determination of Sample Size

A total of up to 24 subjects with renal impairment (up to 8 subjects with severe impairment, and, if necessary, up to 8 subjects with moderate impairment, and/or up to 8 subjects with mild impairment, per eGFR using the CKD-EPI equation) and approximately 8 to 24 matched-control healthy subjects with normal renal function will be enrolled in the study with the goal of having at least 6 subjects from each renal impairment group enrolled in the study and at least 6 subjects with normal renal function complete the study. The sample size chosen for this study was based upon precedent set by other PK studies of similar nature and was not based on power calculations to detect statistically significant differences among groups. This number is considered a sufficient sample size to evaluate the PK of LOXO-305 under various degrees of renal function.

